## PROTOCOL SUMMARY

Title	A double-blind, randomized controlled trial of ATI-450 in patients with moderate-severe COVID-19
Protocol Number	IIT-2020-ATI-450-COVID-19
Phase	2a
Design	Phase 2a, randomized, double-blind, placebo controlled, parallel group study in patients with moderate to severe COVID-19
Study Duration	9 months
Study Center(s)	The University of Kansas Medical Center
Objectives	
Primary Objective To assess the efficacy of ATI-450 on hypoxic respiratory failure-free survival in patients with moderate-severe COVID-19
 
Secondary Objectives To assess the clinical efficacy of ATI-450 on respiratory function and survival in patients with moderate-severe COVID-19
 
To assess the anti-inflammatory and immune effect of ATI-450
 
To assess the safety of ATI-450 in patients with moderate-severe COVID-19
 
Exploratory Objective To assess the pharmacodynamics of ATI-450 in patients with moderate-severe COVID-19

Number of Participants	20
Diagnosis and Main Inclusion Criteria	
Has laboratory-confirmed COVID-19 coronavirus infection as determined by polymerase chain reaction (PCR), or other commercial or public health assay in nasopharyngeal testing within 14 days of enrollment AND,
 
Hospitalized as a result of symptoms and signs related to COVID-19 infection, and ≤14 days since positive test AND:
 
Evidence of hypoxic respiratory failure: SpO2 ≤93% on room air or supplemental oxygen, or SpO2 ≥93% requiring ≥ 2L O2, or PaO2/FiO2 ratio <300mmHg, or tachypnea (respiratory rate ≥ 30 breaths/min) and
 
Evidence of pulmonary involvement by chest imaging or pulmonary exam

Study Product(s), Dose, Route, Regimen	
Dose of ATI-450
 
50 mg (as determined from Phase I study) per dose. (100 mg per day).
 
or
 
Placebo

	
Route Oral tablet
 
Schedule Pill will be taken twice daily preferably spaced 12 ±1 hours apart.

Duration of Administration	Up to a maximum of 14 days while inpatient. Patients discharged home or new requirement for mechanical ventilation will be discontinued off drug permanently.
Interim Monitoring	The study will be monitored at appropriate intervals, no less than those assigned per risk level designation, to assure compliance to GCP and to assess the data quality and study integrity.

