Statistical Methodology	
Details of the statistical analyses and summaries will be provided in the study-specific statistical analysis plan (SAP).
 
Determination of Sample Size Data from 36 patients (18 randomized to ATI-450 and 18 to Placebo) provide enough precision to ensure that the expected asymmetric 70% confidence interval for the difference in the proportion of responders will be no wider than 31 percentage points. This level of precision for the planned 70% confidence interval will facilitate development decisions in accordance with the methods of Frewer et al.
 
Analysis Populations
 
 
• The Full Analysis Set (FAS) will include all patients who have been administered at least one dose of study medication.
 
• The Per-Protocol population will include all FAS patients who have completed their Day 14 visit, and have continued study drug administration through Day 14, or were discharged with a successful outcome prior to day 14.
 
 
Efficacy Analyses and Summaries
 
Primary Efficacy Analysis The primary assessment of efficacy for this study will be the point estimate and corresponding asymmetric 70% confidence interval for the difference in proportions of responders between the ATI-450 and Placebo groups. All subjects who are alive, free of respiratory failure (do not require supplemental oxygen) and do not experience negative intercurrent events by Day 14 of the trial will be considered responders. The point estimate and corresponding 70% confidence interval will be derived using a logistic regression model that includes treatment group, baseline age group (<60 versus ≥60), and gender as factors.
 
Secondary Efficacy Analyses Supportive analyses will be conducted on the secondary efficacy endpoints described in Section 3.5. Categorical variables will be analyzed using a logistic regression similar to that described for the primary

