### 10.2.1 Overall Survival Follow Up (OS-FU)

Participants will be followed for survival status until 60 days post hospital day 1 ( $\pm 3$  days) after end of treatment.

Assessment of survival may be completed by phone contact. Death information from public sources, (e.g. death registry, obituary listing, etc.), can also be used when it is available and verifiable.

Patients who are discharged from the hospital to home or another facility (i.e. rehab, SNF) before reaching day 14 of the study in the hospital will be contacted by a study team member by phone in order to collect patient vital status, oxygenation requirements (i.e. on room air, nasal canula, O2 flow rate), assess for any new adverse events or severe adverse events. Patients who cannot (or are unwilling) to return for day 28 or day 45 in-person follow-up visits will be contacted by phone call. Attempts will need to be made to try and collect study specimens and research labs at the appropriate times, if possible. Attempts will also be made to collect any outside records of laboratory data fulfilling study requirements.

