### 11.4 Participant Discontinuation/Withdrawal from the Study

- Duration of therapy will depend on individual response, evidence of disease progression and tolerance. Any one of the listed items below will be defined as a stopping criteria event. Participants will be removed from protocol therapy for any of the unacceptable adverse event listed below. Participants will have study treatment withdrawn but will remain in the study for follow-up, if any of the following occur:
  - Intubation and ventilation
  - Intercurrent illness that prevents further administration of treatment.
  - Unacceptable adverse event(s) defined as:
    - Malignancy (except for non-melanoma skin cancers)
    - Hepatitis B re-activation
    - Rhabdomyolysis
    - Demyelinating disease
    - Heart failure
    - Lupus-like syndrome

- Hypersensitivity reaction
- Gastrointestinal perforation
- WBC  $<1 \times 10^3/\mu\text{l}$
- ANC  $<0.5 \times 10^3/\mu\text{l}$
- Platelet count  $<50 \times 10^3/\mu\text{l}$
- Hemoglobin:  $<6.5 \text{ g/dl}$
- AST, ALT:
  - $>5 \times \text{ULN}$
  - $>3 \times \text{ULN}$  and (total bilirubin  $>2 \times \text{ULN}$  or international normalized ratio [INR]  $>1.5$ )
  - $>3 \times \text{ULN}$  with appearance of fatigue, nausea, vomiting, right upper quadrant pain or tenderness, fever, rash and/or eosinophilia ( $>5\%$ )
- Serum creatinine:  $>2 \times \text{ULN}$
- Serious bacterial or fungal infection
- Other major developing illness or conditions at the discretion of the treating physician
- Participant demonstrates an inability or unwillingness to comply with the oral medication regimen and/or documentation requirements
- Participant decides to withdraw from the protocol therapy
- General or specific changes in the participant's condition render the participant unacceptable for further treatment in the judgment of the treating investigator
- Major violation of the study protocol (i.e., unable to adhere to study schedule) that in the opinion of the treating investigator, puts the participant at undue risk
- Discontinuation of the study by KUMC
- Confirmed pregnancy
- Completed Overall Survival (OS) follow up as per protocol
- Lost to follow-up
- Death

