#### 15.2 Study Populations

##### Analysis Populations

- The Full Analysis Set (FAS) will include all patients who have been administered at least one dose of study medication. The FAS will be used for the efficacy analyses and summaries. The FAS will be analyzed/summarized as randomized.
- The Per-Protocol population will include all FAS patients who have completed their Day 14 visit and have continued study drug administration through Day 14 or were successfully discharged prior to Day 14. The Per-protocol population will be used for the primary efficacy analysis. Summaries and analyses using the per-protocol population will be done as treated.

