#### 15.5 Intercurrent Events and Missing Data

An intercurrent event is one that occurs after the first dose of study medication and either precludes the observation of the variable or affects its interpretation. The following is a list of negative intercurrent events related to the primary endpoint:

- Death
- Withdrawal from study
- Intubation and ventilation
- Rescue with a non-protocol specified treatment for cytokine release syndrome

The following is a list of positive intercurrent events related to the primary endpoint:

- Early discharge due to recovery

The patient will be considered a responder if the primary endpoint is missing following a positive intercurrent event. Patients will be considered a non-responder for all observations (missing or not missing) following a negative intercurrent event.

Missing data and intercurrent event imputation will be treated in a similar manner as the primary endpoint for secondary endpoints of a categorical nature. For secondary endpoints of a continuous nature, the last observation prior to the intercurrent event will be carried forward (LOCF) for all positive intercurrent events and the worst observation prior to the intercurrent event will be carried forward (WOCF) for all negative intercurrent events.

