Sample Size Justification

Data from 20 patients (10 randomized to ATI-450 and 10 to Placebo) provide some preliminary information about the efficacy and safety of ATI-450. No hypothesis will be formally tested. The mean and exact 90% confidence intervals for within-group event rates will be estimated and no between group difference will be estimated.

Randomization and Blinding

Prior to the start of the study, the University of Kansas Medical Center will generate a list of randomization numbers that shall be transmitted to the assigned clinical packaging organization for study medication labeling. The randomization list will be stored with access limited to designated personnel for study medication labeling. The randomization list will be made available, as appropriate, to unblind the database.

In the treatment period, subjects will be assigned to 1 of the 2 treatment groups in a random manner and at a 1:1 ratio stratified by baseline age group (<60 versus \geq 60). At the Day 1 visit an investigational center staff member will assign study medication to eligible subjects by selecting an appropriate Subject Kit. The staff member must select Subject Kits in chronological sequence and in an ascending numerical order starting with the lowest available Subject Kit number. No Subject Kit number may be omitted or reused. The Subject Kit number is the randomization number.

This study uses a double-blind design. The study medications are indistinguishable in appearance, as packaged and labeled.

Analysis populations

- The Full Analysis Set (FAS) will include all patients who have been administered at least one dose of study medication. The FAS will be population used in the primary efficacy analysis. The FAS will also be the population used secondary efficacy analyses and summaries as well as the population used in all safety summaries. The FAS will be analyzed/summarized as randomized when applied to efficacy endpoints. The FAS will be analyzed/summarized as treated when applied to safety endpoints.
- The Per-Protocol population will include all FAS patients who have completed their Day 14 visit and have continued study drug administration through Day 14 or were successfully discharged prior to Day 14. The Per-protocol population will be used for the primary efficacy analysis. Summaries and analyses using the per-protocol population will be done as treated.

Statistical Analysis Methods

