Missing data for binary secondary endpoints will be treated in a similar manner as the primary endpoint. For secondary endpoints of a continuous nature, the last observation prior to the intercurrent event will be carried forward (LOCF) for all positive intercurrent events and the worst observation prior to the intercurrent event will be carried forward (WOCF) for all negative intercurrent events.

Primary efficacy analysis will be done on the Full Analysis Set (FAS) and the per protocol population. Secondary efficacy analyses and safety analysis will be done on FAS only.

The statistical analyses and summaries will be conducted with the SAS® software package version 9.4 or higher.

Attachments:

- *IIT-2020-ATI-450-COVID-19 _DSMB_AdverseEventListingShell.xls*
- *IIT-2020-ATI-450-COVID-19 DSMB ReportTableShells_2020_1008.doc*

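### The per-protocol set shares primary status with the full analysis set, yet entry to it depends on the outcome: in-hospital deaths and nearly all intubations drop out, while early recoveries stay in

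*SAP*

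**What the plan says.** Protocol 15.2 assigns efficacy analyses to the FAS and then adds: "The Per-protocol population will be used for the primary efficacy analysis". The SAP, under Analysis populations, first gives the primary efficacy analysis to the FAS and in the next bullet repeats that sentence for the per-protocol set. Its closing section, Missing Data Imputation, says: "Primary efficacy analysis will be done on the Full Analysis Set (FAS) and the per protocol population". Neither document calls one set main and the other supportive. They also differ in arm assignment: for efficacy the FAS is analysed as randomised, the per-protocol set as treated.

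Per-protocol entry has two routes. The first is in the SAP: "The Per-Protocol population will include all FAS patients who have completed their Day 14 visit and have continued study drug administration through Day 14". The second is successful discharge before Day 14, which the Protocol Summary words as patients who "were discharged with a successful outcome prior to day 14".

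On the outcome side, Protocol 15.5 lists death, study withdrawal, intubation with ventilation, and non-protocol rescue for cytokine release syndrome as negative intercurrent events, with the rule: "Patients will be considered a non-responder for all observations (missing or not missing) following a negative intercurrent event". The SAP repeats it. Early discharge due to recovery is the positive event, and a missing endpoint after it counts as response.

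On drug status, the Protocol Summary states: "Patients discharged home or new requirement for mechanical ventilation will be discontinued off drug permanently". Protocol 11.4 lists intubation among the stopping events and says: "Participants will have study treatment withdrawn but will remain in the study for follow-up, if any of the following occur".

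**The concern.** A per-protocol set should be defined by adherence and eligibility. Here, staying on drug through Day 14 is partly a consequence of the outcome. Death ends dosing, and intubation stops it under the protocol's own rule. Both are components of the endpoint, and both cost the patient a place in the set. The patient who stops drug because of recovery is excused. The Protocol Summary's wording makes a good outcome an explicit entry condition.

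Intubated patients remain in follow-up, so their outcome is not missing. It is known to be non-response and is left out by the definition of the set.

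The plan can therefore produce two primary results that disagree, one of which tends to flatter each arm, and it does not say which governs. With about 10 patients per arm, one or two exclusions visibly move the reported proportion.

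**Working it through.** No sample size, power or precision figure in the documents bears on this point, so there is no stated figure to reproduce. The check has two parts: who is in the set, and how far the rate can move.

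**Membership against outcome**

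| Course up to Day 14 | Primary outcome | In per-protocol set? |
|---|---|---|
| Dies in hospital before Day 14 | Non-responder | No |
| Intubated, drug stopped | Non-responder | No, unless successfully discharged before Day 14 |
| Withdraws from study before discharge | Non-responder | No |
| Drug stopped for toxicity or infection, not discharged by Day 14 | Depends on Day 14 status | No |
| On drug and on oxygen at Day 14 | Non-responder | Yes |
| Non-protocol rescue, drug continued | Non-responder | Yes |
| Successful early discharge, then fails by Day 14 | Non-responder | Yes |
| Discharged early because recovered, endpoint missing | Responder | Yes |
| Sent home on oxygen before Day 14 | Depends on Day 14 status | Unclear: successful discharge is not defined |

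Failure after discharge can be seen, because Protocol 10.2.1 has "Patients who are discharged from the hospital to home or another facility (i.e. rehab, SNF) before reaching day 14 of the study" contacted by phone for vital status and oxygen use.

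**Effect on one arm**

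Inputs: n = 10 per arm (SAP, Sample Size Justification); exact 90% Clopper-Pearson intervals (SAP, Primary Efficacy Analysis); a 50% response rate (Protocol 15.1, stated there for placebo only). The number of patients removed is an assumption.

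With R responders in the FAS, k non-responders removed and j responders removed, the per-protocol rate is (R − j)/(n − j − k). It exceeds the FAS rate R/n when k/(n − R) > j/R, that is, when a larger share of failures than of responders is removed. The exact limits for x of m are the 5% quantile of Beta(x, m − x + 1) and the 95% quantile of Beta(x + 1, m − x).

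| Failures removed (j = 0) | Rate | Exact 90% CI |
|---|---|---|
| 0 (FAS) | 5/10 = 50.0% | 22.2 to 77.8% |
| 1 | 5/9 = 55.6% | 25.1 to 83.1% |
| 2 | 5/8 = 62.5% | 28.9 to 88.9% |
| 3 | 5/7 = 71.4% | 34.1 to 94.7% |
| 4 | 5/6 = 83.3% | 41.8 to 99.1% |
| 5 | 5/5 = 100% | 54.9 to 100% |

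The last row needs every failure to be of a removed type. Removing one responder and no failure works the other way: 4/9 = 44.4%.

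**Effect on the comparison of arms**

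Assume FAS rates of 70% and 50%, a difference of +20 points; the 70% is in neither document. If the same fraction f of non-responders is removed from both arms and no responders are, each rate becomes p/[p + (1 − p)(1 − f)]:

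- f = 0.25: 75.7% v 57.1%, +18.5 points
- f = 0.50: 82.4% v 66.7%, +15.7 points
- f = 0.75: 90.3% v 80.0%, +10.3 points
- f = 1: 100% v 100%, 0 points

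Equal removal therefore shrinks the difference but does not reverse it. Reversal needs unequal removal: taking out 1 of 3 active failures and 4 of 5 placebo failures gives 7/9 − 5/6 = 77.8% − 83.3% = −5.6 points. Over all 24 combinations, 7/(10 − a) − 5/(10 − b) with a = 0 to 3 and b = 0 to 5, the difference runs from 7/10 − 5/5 = −30 to 7/7 − 5/10 = +50 points. Six are negative, one is zero, seven lie between 0 and +20, one equals +20 and nine exceed +20. These are possible values, not probabilities.

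**The case against.** The strongest reply is that little turns on this. The study is hypothesis generating, with no formal test, no multiplicity control and no label claim. The FAS primary result will always be produced, and secondary efficacy (including mortality) and safety use the FAS only. All of that is true. It rules out any claim of hidden deaths or type I error inflation, and it limits the seriousness. It gives no reason for the per-protocol set to hold primary status.

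The selection is also incomplete. Patients still on oxygen and drug at Day 14 remain as failures. A patient intubated and then successfully discharged before Day 14 could remain, as could one first intubated on Day 14 itself. These are edge cases. The entry sentence can also be read as requiring the Day 14 visit of everyone, including early discharges. The commas in the Protocol Summary favour the reading used here, and the schedule of events moves the Day 14 assessments to discharge, which brings the two readings together. In-hospital deaths are out on either.

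On size, removing one or two failures gives intervals that overlap the FAS interval almost entirely. Protocol 5.2 excludes patients expected to die or need ventilation within 48 hours, so the large shifts may be unlikely. That stands, and it is why the figures are given as a range. Finally, the SAP says no between-group difference will be estimated for the primary endpoint, so the contrast figures are secondary to the per-arm ones. They still matter, because Protocol 15.3 plans a difference and the two arm rates will be read side by side.

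**Conclusion.** The concern holds. Two populations share the primary efficacy analysis without ranking, and one of them removes in-hospital deaths and nearly all intubations, which the plan itself defines as non-response, while keeping early recoveries. The per-protocol proportion is higher than the FAS proportion whenever failures are removed at a higher rate than responders. In an arm with 5 of 10 responding, each of the first three failures removed adds about 6 to 9 points. The definitions establish the selection; its size rests on assumed event counts and, for the contrast, on an assumed 70% active rate. This should be fixed. It does not invalidate the trial, because the FAS analysis is already planned.

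**What to change.** In the Protocol Summary, Protocol 15.2 and both places in the SAP (Analysis populations and the closing section), name the FAS, analysed as randomised, as the only primary efficacy population and label the per-protocol set supportive. Delete the sentence that gives the per-protocol set the primary analysis.

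Beside any per-protocol result, report by arm how many FAS patients were excluded and why: death, intubation, study withdrawal, other stop of study drug, or discharge not counted as successful. Define successful discharge for this purpose, and describe the set as outcome-dependent.

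Optionally, redefine the set by eligibility and dosing adherence up to the first of death, intubation, a protocol-mandated stop, discharge or Day 14, so that deaths and intubations stay in as non-responders. That takes more work, because adherence criteria would have to be written, and the main fix does not depend on it.

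The main fix costs wording changes and one table. It needs no new data.

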##### 3.2.1 PRIMARY ENDPOINT

What is being measured	Measurement time frame	Measurement Tool
Proportion of responders on Day 14 defined as all subjects who are alive, free of respiratory failure (do not require supplemental oxygen) and do not experience negative intercurrent events by Day 14 of the trial will be considered responders. 	Study Day 14	Noted in patient medical record or Day 14 Follow-up call

 Patients with pre-existing oxygen requirements who return to at least their baseline pre-COVID-19 infection oxygenation level will be considered to have successfully achieved the respiratory-free failure survival endpoint.

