The primary objective is to assess the efficacy of ATI-450 on hypoxic respiratory failure-free survival in patients with moderate-severe COVID-19 pneumonia at day 14.

Secondary Objectives:

- To assess the clinical efficacy of ATI-450 on respiratory function and survival in patients with moderate-severe COVID-19 pneumonia.
- To assess the safety of ATI-450 in patients with moderate-severe COVID-19 pneumonia.

Exploratory Objectives:

- To Assess the pharmacodynamics of ATI-450 in patients with moderate-severe COVID-19 pneumonia.

Outcome Measures

Primary Efficacy Measure

- Primary treatment responder: defined as any patient who is alive, free of respiratory failure (does not require supplemental oxygen (greater than pre-existing use)) and does not experience a negative intercurrent event on Day 14 of the trial.

An intercurrent event is one that occurs after the first dose of study medication and either precludes the observation of the primary variable/endpoint or affects its interpretation. The following is a list of negative intercurrent events that could occur during this study:

- Death
- Withdrawal from study
- Intubation and ventilation
- Rescue with a non-protocol specified treatment for cytokine release syndrome

The following is a list of positive intercurrent events that could occur during this study:

- Early hospital discharge due to recovery

A patient will be considered a treatment responder if the primary endpoint is missing following a positive intercurrent event. A patient will be considered a treatment non-responder for all observations (missing or not missing) following a negative intercurrent event.

Secondary Efficacy Measures

- Change from baseline in the WHO COVID-19 7-point ordinal scale over time (**BASELINE, DAY 7, DAY 14, DAY 28**).
- All-cause mortality through Day 60 (**DAY 7, DAY 14, DAY 28 AND FOLLOW-UP**.).
- Responder based on 7-point ordinal scale: Greater than 2-point improvement from baseline on the 7-point ordinal scale. (**BASELINE, DAY 7, DAY 14, DAY 28 AND FOLLOW-UP**.).
- Time to discharge from the hospital.

Safety assessments include:

- Adverse events

Exploratory measures include:

- Change in serum cytokine Interleukin (IL)-6 over time (baseline, d7, EOT, d28).
- Change in serum cytokine IL-8 over time (baseline, d7, EOT, d28).
- Change in serum cytokines IL-1 β over time (baseline, d7, EOT, d28).
- Change in serum cytokine Tumor Necrosis Factor (TNF- α) over time.

*EOT: end of treatment

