Descriptive statistics (number of observations, mean (standard deviation) or median (minimum, maximum)) will be provided for continuous variables, and counts and percentages will be presented for categorical variables for each group.

Primary Efficacy Analysis

The study is hypothesis generating. The primary assessment of efficacy for this study will be the point estimate and corresponding exact 90% confidence interval for the proportions of responders for the ATI-450 and Placebo groups. All subjects who are alive, free of respiratory failure (do not require supplemental oxygen) by Day 14 of the trial will be considered responders. The point estimate and corresponding 90% confidence interval will be derived based on sample proportions and the Copper-Pearson CIs for proportions for the two groups (categorical data analysis by Alan Agresti, 3rd edition).

Secondary Efficacy Analyses

Binary variables will be analyzed using the method like that described for the primary endpoint. In addition to the point estimate and confidence interval for the difference in proportions for binary endpoints, odds ratios, corresponding confidence intervals will be provided. For binary measures that are recorded over time, separate analyses will be conducted at each timepoint.

Continuous secondary efficacy endpoints will be analyzed by estimating group means and mean difference and 95% CIs at each time point. Missing data will be imputed with the single imputation methods described above (LOCF or WOCF).

For time to discharge from hospital, estimates of the median (50th percentile) will be provided for each treatment group and Kaplan-Meier Curves will be provided. A two-sided stratified log-rank test will be applied. The stratification factor will be baseline age group (<60 versus ≥ 60).

Exploratory Outcomes Analyses

For all the Cytokines, changes over time (baseline, d7, EOT, d28) will be summarized by descriptive statistics and trajectory plots. Any time point after the end of treatment (EOT) will not be measured.

Safety Summaries

AEs will be summarized using table format based on DSMB requirements (attached).

Missing Data Imputation

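### The primary analysis text drops the pre-existing-oxygen allowance, and imputed success after discharge for recovery carries no oxygen condition

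*SAP*

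**What the plan says.** The SAP describes a responder twice. Under Primary Efficacy Measure, the patient must be alive and is one who "does not require supplemental oxygen (greater than pre-existing use)) and does not experience a negative intercurrent event on Day 14 of the trial". Under Primary Efficacy Analysis, the text is: "All subjects who are alive, free of respiratory failure (do not require supplemental oxygen) by Day 14 of the trial will be considered responders". Protocol 15.3 uses the same short form. The footnote to protocol 3.2.1 carries the allowance: it counts as successes "Patients with pre-existing oxygen requirements who return to at least their baseline pre-COVID-19 infection oxygenation level".

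Two general rules follow the SAP's fuller definition. One reads: "A patient will be considered a treatment non-responder for all observations (missing or not missing) following a negative intercurrent event". The other reads: "A patient will be considered a treatment responder if the primary endpoint is missing following a positive intercurrent event". Protocol 15.5 matches the second: "The patient will be considered a responder if the primary endpoint is missing following a positive intercurrent event". The only positive event that 15.5 lists is "Early discharge due to recovery", and the SAP lists the same event in nearly the same words.

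For the source of the Day 14 status, protocol 3.2.1 gives: "Noted in patient medical record or Day 14 Follow-up call". Section 10.2.1 plans a telephone contact for patients discharged before Day 14, covering vital status and oxygen needs. The Schedule of Events (10.4) has early-discharged patients complete the Day 14 assessments at discharge, and its footnotes ask for daily oxygen supplementation in hospital.

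**The concern.** The primary result is one responder proportion per arm with an exact 90% interval, so it depends entirely on who is counted in the numerator.

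First, the section a programmer would work from leaves out a condition that the formal definition contains. A home-oxygen user who has returned to the usual level would be classified differently depending on which section is followed, and no text says which governs.

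Second, being off supplemental oxygen beyond prior use is the core of the endpoint, yet the rule that fills in a missing Day 14 value as success does not look at oxygen. If the discharge record shows new oxygen and nobody reaches the patient later, the rule can return a success although the oxygen condition was not met when the patient was last seen. The SAP treats missing binary secondary endpoints in a similar way, so the gap is not confined to the primary endpoint.

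No formal test is planned, so what is at stake is the accuracy of the reported rates and intervals.

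**Working it through.** **Definitions side by side**

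| Place | Pre-existing-oxygen allowance | Clause on negative intercurrent events |
|---|---|---|
| SAP, Primary Efficacy Measure | yes | yes |
| SAP, Primary Efficacy Analysis | no | no |
| Protocol 3.2.1 | yes (footnote) | yes |
| Protocol 15.3 | no | no |
| Protocol Summary, Statistical Methodology | no | yes |

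The two gaps differ in consequence.

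- *Intercurrent events.* The general rule in the SAP and in protocol 15.5 makes anyone with a negative event a non-responder from then on. The missing clause changes no classification and is only wording to align.
- *Oxygen.* No rule outside the definitions settles the matter. Take a patient on home oxygen before infection who is back at that level on Day 14. The Primary Efficacy Measure and the 3.2.1 footnote give responder; the literal text of the Primary Efficacy Analysis and 15.3 gives non-responder. Such patients can enrol: the exclusion criteria in 5.2 do not bar home oxygen, and the footnote anticipates them.

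**The missing-data rule, step by step**

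1. It applies only if the patient left hospital early because of recovery. Neither document defines recovery or links it to oxygen use.
2. It applies only if the Day 14 status is still missing after the medical record and the follow-up call have been used.
3. When both hold, the patient is a responder. Oxygen use recorded at discharge or on the last hospital day is not consulted.

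A patient discharged on new oxygen, classed as recovered and not reached afterwards is therefore scored a success.

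**Size per patient**

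Inputs: n = 10 per arm (SAP, Sample Size Justification) and an exact Clopper-Pearson 90% interval (SAP, Primary Efficacy Analysis). The starting point of 5/10 is an illustration, equal to the 50% placebo rate assumed in protocol 15.1. The SAP states no expected rate or width to reproduce.

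One patient = 1/10 = 10 percentage points.

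For x responders out of n, the lower limit is the 5th percentile of Beta(x, n − x + 1), and the upper limit is the 95th percentile of Beta(x + 1, n − x).

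| Case | Responders | Rate | 90% CI |
|---|---|---|---|
| Starting point | 5/10 | 50% | 22.2–77.8% |
| One home-oxygen patient scored by the short text | 4/10 | 40% | 15.0–69.6% |
| One patient on new oxygen imputed as success | 6/10 | 60% | 30.4–85.0% |

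The documents do not say how many patients are in either situation, so no total is projected.

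**The case against.** The best reply on the first part is that the Primary Efficacy Measure is the SAP's formal definition, the 3.2.1 footnote is explicit, and the analysis paragraph merely abbreviates them. A sensible statistician would probably follow the fuller text. That supports the proposed correction, but it does not remove the conflict: followed as written, the analysis paragraph misclassifies home-oxygen patients.

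On the second part, several conditions must coincide. The patient must leave on new oxygen, still be classed as recovered, and be missed by both the call and the record. Recovery could be read to exclude anyone sent home on new oxygen. The Day 14 assessments done at discharge might be taken as the Day 14 value, in which case nothing is missing. The documents settle neither point. Oxygen use at an earlier discharge also does not prove failure on Day 14, because the patient may have weaned. All this narrows the problem, but the choice of reading is left open until data are in hand.

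The rule might also be defended because the 50% benchmark in protocol 15.1 counts patients out of hospital with no stated oxygen condition. The trial's own endpoint does have that condition, and the SAP's sample-size text no longer uses the benchmark.

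Three stronger readings are tempting and are not supported:

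- *Every early discharge with a missing Day 14 counts as success.* The rule is limited to discharge for recovery.
- *Oxygen after discharge goes uncollected.* Section 10.2.1 plans to ask about it by telephone.
- *The short text lets intubated or rescued patients count as responders.* The general non-responder rule still applies to them.

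**Conclusion.** The concern holds in two limited parts.

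The first is a definite inconsistency: the SAP's Primary Efficacy Analysis and protocol 15.3 omit the allowance that the SAP's Primary Efficacy Measure and protocol 3.2.1 contain, and the omission changes the classification of home-oxygen patients.

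The second is a gap in specification. Recovery is undefined and the imputation carries no oxygen condition, so success can be imputed against recorded oxygen use. This reaches only patients whose Day 14 status neither the call nor the record supplies.

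The size is 10 percentage points per affected patient in an arm of 10, downward for the first part and upward for the second. This assumes the SAP's 10 per arm; the intervals shown also assume a 5/10 starting point. With no affected patients the effect is zero. The study is hypothesis generating with no formal test, so no error rate is at issue. The correction is worth making because these two proportions are the whole primary result and the change costs little.

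**What to change.** 1. In the SAP's Primary Efficacy Analysis and protocol 15.3, use the fuller definition: alive, no oxygen above pre-COVID use on Day 14, and no negative intercurrent event from first dose through Day 14. Make the Protocol Summary match.
2. In the SAP's Primary Efficacy Measure and protocol 15.5, keep the positive-event rule limited to early discharge for recovery. For this analysis rule only, count a discharge as recovery if the last recorded oxygen status, from the discharge assessment or a later call, was room air or no more than pre-COVID use. Score other patients with missing Day 14 status as non-responders. This governs scoring, not when a patient is discharged.
3. Report the number of imputed responders per arm, with one sensitivity line counting all of them as non-responders.

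The cost is a few sentences in each document and one extra table line. Discharge and telephone oxygen data are already planned; the pre-COVID level would come from the medical history.

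There are two downsides. The responder rate may be slightly lower, and so further from the discharge-based benchmark in protocol 15.1. And a patient discharged on oxygen who weaned by Day 14 but was not reached would be counted as a non-responder.
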